[figure not shown]

## 1 SYNOPSIS

Title of Study:	RESTOR: A Multicenter, Randomized, Double-Blind, Placebo-Controlled Efficacy, Tolerability and Safety Study of DFN-11 Injection (Sumatriptan 3 mg) in Episodic Migraine With or Without Aura
Protocol Number:	DFN-11-CD-004
Investigators/Study Sites:	Approximately 18 sites in United States of America
Phase of Development:	3
Objectives:	
Primary Objective
 
Double-Blind (Period 1)
 

• To assess the proportion of subjects who are pain-free at 2 hours postdose in the double-blind period

 
Key Secondary objectives
 
Double-Blind (Period 1)
 

• To assess the proportion of subjects who are pain-free at 1 hour postdose

• To assess the proportion of subjects with their most bothersome symptom (MBS) among nausea, photophobia, and phonophobia, absent at 2 hours postdose

 
Other Secondary Objectives
 
Double-Blind and Open-Label Extension (Period 1 and Period 2)
 

• To assess the proportion of subjects who are free from nausea, photophobia, and phonophobia

• To assess the proportion of subjects who have pain relief

• To assess the proportion of subjects who are pain-free

• To assess the proportion of subjects with their MBS absent

• To assess change in functional disability score

- To assess the proportion of subjects who have sustained pain freedom [REDACTED]
- To assess the proportion of subjects who use a second dose of the study medication or rescue medication after 2 hours (2-24 hours) postdose
- To assess treatment satisfaction at 2 hours postdose (7 point scale)
- To assess treatment satisfaction as measured by Patient Perception of Migraine Questionnaire-Revised (PPMQ-R) at 24 hours postdose
- To evaluate safety and tolerability

**Exploratory Objectives**

Study Design:	
This is a randomized, double-blind study, with an open-label extension, to be conducted at approximately 18 centers in the United States (US). Male and female subjects, 18-65 years old (inclusive), previously diagnosed with episodic migraine (at least 12 months medical history prior to screening) who do not have medication overuse headaches (MOH), who experience 2 to 6 migraine attacks (with or without visual aura) per month, with 14 or fewer migraine headache days per month, and who can demonstrate 48 hours of headache free time between migraine attacks, will be initially randomized in a 1:1 ratio in a double-blind fashion to receive by subcutaneous (SC) injection either DFN-11 or placebo, to be used in 1 migraine attack within 1 hour of experiencing moderate to severe pain level. This double-blind period is up to 4 weeks (+ 3 days) or within 5 days (+ 3 days) postdose, whichever is earlier, depending on when, and if, the subject will get migraine attack during the double-blind period. Subjects may subsequently continue into an open-label period where they will receive active DFN-11 for 8 weeks to treat their migraine within 1 hour of migraine pain onset at any pain level.
 
During the 2 treatment periods, data regarding the study medication effect and the associated impact on function and subjects' satisfaction will also be collected. All subjects will receive the study medication via self-administered SC injections (DFN-11 or placebo) using an autoinjector during the study. After study completion or discontinuation, subjects should be referred to their usual healthcare professional to resume pre-study standard of care, as per the Investigator's discretion. Subjects will return the autoinjector to the study site at the end of the study.
 
During both treatment periods of the study, subjects will have an option to take another dose of study medication, if they experience relief but feel the first dose is insufficient, or rescue medication 2 hours after the first dose of study medication if required and after the efficacy data has been recorded. No more than 2 doses of study medication will be taken in a 24 hour period. Rescue medication will be decided between the Investigator and the subject.

Selection of Subjects:	
Main Inclusion Criteria:
 
Subjects may be included in the study if they meet the following criteria:

	

1. Able and willing to provide written informed consent

2. Male or female, 18 to 65 years of age, inclusive, at screening

 
Notes:
 

a. If female, a subject must have a negative serum pregnancy test at screening, does not plan to become pregnant during the study, and is not lactating

b. If female, a subject also must have a negative urine pregnancy test at all subsequent study visits after the Screening Visit, and agree to practice a reliable form of contraception or abstinence during the study (except if surgically, or otherwise, sterile or >1 year post-menopausal). Acceptable forms of contraception include implants, injectables, combined oral contraceptives, an intrauterine device, a vasectomized partner, an exclusively female partner, and double-barrier methods.

c. If male (with female partner), a subject must agree to practice a reliable form of contraception or abstinence during the study.

 

3. A history of episodic migraine (using International Classification of Headache Disorders criteria, 2nd edition [ICHD II]) who experience 2 to 6 migraine attacks a month for at least the past 12 months with no more than 14 migraine headache days per month, and with 48 hours of headache free time between migraine headaches

4. Have migraine with or without aura; if with aura, the aura cannot last longer than 60 minutes

5. Subjects who, in the opinion of the Investigator, are willing and able to:

• Evaluate and record pain, migraine symptoms, and study medication effectiveness information in real time using a subject eDiary for the duration of the study

• Record each instance of the use of study medication and rescue medication in real time using a subject eDiary for the duration of the study

• Comply with all other study procedures and scheduling requirements

--	--

	
6. In the opinion of the Investigator, subjects understand and are able to use SC device correctly after instructions from the study site staff
 
Main Exclusion Criteria:
 
Subjects will be excluded from participating in the study if they meet any of the following criteria:
 

1. Minors, even if they are in specified study age range

2. Medication overuse headache as defined by ICHD II:

• Opioids <math>\geq</math> 10 days a month during the 90 days prior to screening

• Combination medications (e.g., Fiorinal®) <math>\geq</math> 10 days a month during the 90 days prior to screening

• Nonsteroidal anti-inflammatory drugs (NSAIDs) or other simple medications <math>></math> 14 days a month during the 90 days prior to screening

• Triptans or ergots <math>\geq</math> 10 days a month during the 90 days prior to screening

3. Subjects treated with onabotulinumtoxin A (Botox®) or other botulinum toxin treatment; or history of receiving such treatment during the 180 days prior to screening

4. On unstable dosages of migraine prophylactic medications during the 30 days prior to and through screening

5. Taking mini-prophylaxis for menstrual migraine

6. Subjects with hemiplegic or basilar migraine or other forms of neurologically complicated migraine

7. Subjects who have prolonged aura (i.e., more than 1 hour)

8. Cerebrovascular disease including but not limited to a history of stroke or transient ischemic attack (TIA)

9. A history of migralepsy (seizure following a migraine) or a concurrent diagnosis of seizure disorder

10. Subjects who cannot differentiate between a migraine headache and tension-type or cluster headache or other types of headache

11. Subjects with a history of more than occasional (based on Investigator's judgment) tension-type headache (distinct from migraine headache days count).

--	--

	

12. Subjects with a history of cluster headaches

13. Subjects with the diagnosis of “probable migraine” (ICHD II)

14. Subjects who have intolerance to any formulation of sumatriptan or who have experienced a significant AE related to any other triptan

15. A history of resistance or non-responsiveness to SC sumatriptan (6 mg or lower dose) or non-response to two or more other triptans at an adequate dose and treatment duration in the opinion of the Investigator

16. Ischemic coronary artery disease (CAD): including but not limited to angina pectoris, history of myocardial infarction or documented silent ischemia or coronary artery vasospasm, including Prinzmetal's angina

17. Subjects with Wolff-Parkinson-White syndrome or arrhythmias associated with other cardiac accessory conduction pathway disorders

18. Subjects with a history of congenital heart disease

19. Uncontrolled hypertension or screening systolic blood pressure (SBP) > 140 mmHg or diastolic blood pressure (DBP) > 90 mmHg (the values should be reconfirmed to rule out a transient fluctuation; see Section 7.3 for details).

20. Have peripheral vascular disease including but not limited to ischemic bowel disease (IBD) and Raynaud's disease.

21. Use of monoamine oxidase (MAO) inhibitor at least 30 days prior to screening

22. Have contradictions to SC therapies such as a history of any bleeding disorder or is currently taking an anti-coagulant or any antiplatelet medication; subjects on stable doses of aspirin up to 100 mg/day for cardiac prophylaxis or the occasional use of medications containing a higher dose of aspirin, such as Excedrin, for pain, fever and as rescue medication are allowed

23. Any abnormal physiology and/or pathology which, in the opinion of the Investigator or Sponsor, which would be contraindicated for study participation and would not allow the objectives of the study to be met

24. Subjects who show any clinical laboratory or electrocardiogram (ECG) abnormality that in the opinion of

--	--

	
the Investigator would endanger the subject or interfere with the study conduct. If the results of the clinical laboratory or ECG are outside of normal reference range the subject may still be enrolled but only if these findings are determined to be not clinically significant by the Investigator. This determination must be recorded in the subject's source document prior to enrolment.
 

25. Fridericia's corrected QT (QTcF) interval greater than 450 msec

26. Severe renal impairment (creatinine > 2 mg/dl)

27. Serum total bilirubin > 2.0 mg/dL

28. Serum aspartate aminotransferase (AST), alanine aminotransferase (ALT), or alkaline phosphatase > 2.5 times the upper limit of normal

29. Subjects with uncontrolled diabetes mellitus, or a glycosylated hemoglobin (HbA1c) > 7.0%, or with diabetes mellitus requiring insulin

30. A history of alcohol or substance use disorder according to the Diagnostic and Statistical Manual of Mental Disorders, Edition V (DSM-V) (including marijuana) within 1 year prior to screening

31. Current treatment with antipsychotics or use of antipsychotics within 30 days of screening

32. Subjects with a positive urine drug screen for recreational drugs, alcohol, marijuana (whether legal or not) or for prescription drugs not explained by stated concomitant medications

• Subjects consuming opioids for the treatment of migraine or using opioids or barbiturates temporarily for a legitimate medical cause may participate as long as they do not meet the MOH criteria

• Chronic use of benzodiazepines is allowed if used for legitimate medical use, as long as the regimen has been stable for at least 3 months prior to screening and is expected to remain stable throughout the study

• Chronic use of amphetamines to treat attention deficit disorder (ADD) or attention deficit hyperactivity disorder (ADHD) and related disorders is allowed as long as the regimen has been stable for at least

--	--

	
3 months prior to screening and is expected to remain stable throughout the study
 
Note: For the above-mentioned conditions, the site must have appropriate documentation to justify the mentioned drug use (e.g., documented medical history and a valid prescription-based dispensation)
 

33. A history of or current neurological or psychiatric impairment, including but not limited to psychosis, current major depression, bipolar disorder or cognitive dysfunction that, in the opinion of the Investigator, would compromise data collection

34. Subjects who have received treatment with an investigational drug or device within 30 days of the screening visit or participated in a central nervous system clinical trial in the 3 months prior to screening

35. Subjects with any other medical condition that, in the judgment of the Investigator and/or Medical Monitor, would confound the objectives of the study (e.g., positive screening test for human immunodeficiency virus [HIV], hepatitis B surface antigen positive or hepatitis C positive, a known history of systemic lupus erythematosus)

36. History of cancer within the past 5 years (except adequately treated basal cell or squamous cell skin carcinoma or in situ cervical cancer)

37. History of any skin condition that may adversely affect the injection or use of subcutaneously administered medication such as scleroderma

38. Subjects who should not be enrolled per the precautions, warnings, and contraindications section of the Imitrex® product label or package insert

39. Subjects who plan to donate blood, sperm, or oocytes during the study and for 30 days after the last dose of study medication

40. Subjects who are employees or immediate relatives of the employees of the Sponsor, any of its affiliates or partners, or of the study center

Planned Sample Size:	A total of approximately 266 subjects will be randomized in a 1:1 ratio into 2 treatment arms. The study may be stopped sooner based on an independent Data Monitoring Committee (DMC) recommendation after reviewing study efficacy data

	(see Statistical Methods and Planned Analysis section for details) at an interim analysis (IA).
Investigational Therapy:	DFN-11 Injection (sumatriptan 3 mg)
Reference Therapy:	Placebo injection
Treatment Duration:	The duration of study participation will be approximately 15 weeks, including screening period of approximately 3 weeks, double-blind treatment period of up to 4 weeks (+ 3 days) or within 5 days (+ 3 days) postdose, whichever is earlier, and an open-label treatment period of 8 weeks ( $\pm$ 3 days).
Criteria for Evaluation:	
Efficacy:
 

Subjects will be provided with an eDiary at Screening Visit (Visit 1) to collect at least 1 migraine episode data in real time and, if randomized, to continue to collect migraine data in real time through End of Treatment (ET) Visit (Visit 5/ET):

Migraine pain start and end (date and time)

Level of headache pain predose and at various timepoints postdose (Levels: 0 = none; 1 = mild; 2 = moderate; 3 = severe)

[REDACTED]

Migraine symptoms and MBS other than pain: nausea, photophobia, and phonophobia, predose and at various timepoints postdose

PPMQ-R

Functional disability scale (0 = no disability, able to function normally; 1 = performance of daily activities mildly impaired, can still do everything but with difficulty; 2 = performance of daily activities moderately impaired, unable to do some things; 3 = performance of daily activities severely impaired, cannot do all or most things, bed rest may be necessary)

Treatment satisfaction (7 point scale)

Study medication and rescue use

 
Safety:
 

Adverse events: Adverse events will be collected from signing of the informed consent form (ICF) at Screening Visit (Visit 1) until a subject's completion or discontinuation from the study

Concomitant medication review

	

Physical examinations

Pregnancy tests in females

Measurement of vital signs (sitting systolic and diastolic blood pressure, pulse rate, and body temperature)

Clinical laboratory examination (hematology, chemistry, and urinalysis)

Urine drug screen

12-lead ECG

Study Endpoints:	
Primary Endpoints:
 
Double-Blind Period (Period 1)
 
The proportion of subjects who are pain-free (defined as a reduction from predose moderate [Grade 2] or severe [Grade 3] pain to none [Grade 0]) 2 hours after the first dose of study medication compared between DFN-11 and placebo in the double-blind period.
 
Key Secondary Endpoints:
 
Double-Blind Period (Period 1)
 

• [REDACTED]

• The proportion of subjects who are pain-free (defined as a reduction from predose moderate [Grade 2] or severe [Grade 3] pain to none [Grade 0]) 1 hour after the first dose of study medication compared between DFN-11 and placebo in double-blind period.

• The proportion of subjects who are free from their MBS among nausea, photophobia, and phonophobia 2 hours after the first dose of study medication compared between DFN-11 and placebo in double-blind period.

 
Other Secondary Endpoints:
 
Double-Blind and Open-Label Extension (Period 1 and Period 2)
 
Efficacy Endpoints
 
The secondary efficacy endpoints are as follows:
 

• [REDACTED]

	

• The proportion of subjects who have pain relief [REDACTED]

• The proportion of subjects who are pain-free [REDACTED]

• The proportion of subjects with their MBS absent [REDACTED]

• Change in functional disability score [REDACTED]

• The proportion of subjects who use a second dose of the study medication or rescue medication after 2 hours (2-24 hours) postdose study medication compared between DFN-11 and placebo in double-blind period, and DFN-11

--	---

in the open-label period

- Treatment satisfaction at 2 hours postdose as determined on a 7 point scale after study medication compared between DFN-11 and placebo in double-blind period, and DFN-11 in the open-label period.
- Treatment satisfaction as measured by PPMQ-R at 24 hours postdose study medication compared between DFN-11 and placebo in double-blind period, and DFN-11 in the open-label period.

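### Exclusion criterion 21 has its time window reversed: read literally, it misses recent-only MAO-inhibitor users and excludes remote past users without limit

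*Combined protocol and SAP*

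**What the plan says.** The Main Exclusion Criteria in the Synopsis (under Selection of Subjects) open with "Subjects will be excluded from participating in the study if they meet any of the following criteria". The list is therefore disjunctive: one item met is enough to exclude. Item 21 reads "Use of monoamine oxidase (MAO) inhibitor at least 30 days prior to screening".

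Other items in the same list also place drug exposure in time:

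- Item 2 (medication overuse) counts days of use per month over the 90 days before screening.
- Item 3 (botulinum toxin): "history of receiving such treatment during the 180 days prior to screening".
- Item 4 (prophylactics): "On unstable dosages of migraine prophylactic medications during the 30 days prior to and through screening".
- Item 31 (antipsychotics): "Current treatment with antipsychotics or use of antipsychotics within 30 days of screening".
- Item 34 (investigational products): "Subjects who have received treatment with an investigational drug or device within 30 days of the screening visit".

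No other criterion in the text supplied names MAO inhibitors. Item 38 is a general rule that removes "Subjects who should not be enrolled per the precautions, warnings, and contraindications section of the" Imitrex label or package insert; the label itself is not reproduced. Item 19 tells the reader to "see Section 7.3 for details", so a fuller protocol text exists that was not available here.

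**The concern.** A washout exclusion should remove people who are taking the drug or have taken it recently. Item 21 points the other way: its condition is satisfied by use at a distance of 30 days or more and is silent on anything nearer. Two errors follow. A subject whose only exposure is recent is not excluded by this item, and a subject whose exposure ended long ago is excluded for no evident reason.

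The investigational product is sumatriptan, self-injected by autoinjector, with up to two doses allowed in 24 hours. Anyone who continues into the open-label period receives active drug for 8 weeks, including subjects first randomized to placebo. The screening rule is therefore an important control on MAO-inhibitor exposure, and the sponsor thought it necessary to write a specific one. With about 18 sites applying it, different readings would lead to different decisions on the same kind of subject.

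**Working it through.** The plan has no figure to reproduce. The check applies the rule as written to possible exposure histories and compares the result with the form used in item 31.

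**Notation.** Let *s* be the first day of use and *e* the last day of use, both in days before screening, with *e* = 0 if use is ongoing.

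- Item 21 as written: excluded if any use lies 30 or more days before screening, that is, if *s* ≥ 30.
- Item 31 form (current use, or use within 30 days): excluded if *e* ≤ 30. Whether day 30 itself counts makes no difference below, because no pattern has its last use on that day.

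| Pattern | *s* | *e* | Item 21 as written | Item 31 form | Same? |
|---|---|---|---|---|---|
| A. Remote past use only | 400 | 365 | excluded (400 ≥ 30) | eligible (365 > 30) | no |
| B. Short recent use, stopped | 20 | 10 | not excluded (20 < 30) | excluded (10 ≤ 30) | no |
| C. Just started, ongoing | 7 | 0 | not excluded (7 < 30) | excluded (0 ≤ 30) | no |
| D. Established, ongoing | 60 | 0 | excluded (60 ≥ 30) | excluded (0 ≤ 30) | yes |
| E. Established, recently stopped | 60 | 10 | excluded (60 ≥ 30) | excluded (10 ≤ 30) | yes |

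The patterns were chosen to show where the two rules part and say nothing about how common each is. In general terms, the rules disagree in two regions: *s* < 30, where all use is recent and the literal rule misses it; and *e* > 30, where all use is past and the literal rule excludes it however long ago it was. They agree when use began at least 30 days before screening and continued to within 30 days of it.

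**Is this the document's usual phrasing?** No. Items 2, 3, 4, 31 and 34 all capture a period ending at or running up to screening. Item 4 is a weaker comparator, since it concerns dose stability and not washout, but its window also runs up to screening. Item 32 does ask for at least 3 months before screening, but as a minimum period of stable dosing that permits entry, where such a phrase is right. In a rule that excludes for use, it reverses the window.

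**Would another reading rescue it?** If the phrase is taken to mean use lasting at least 30 days, pattern C (7 days of use) is still not excluded. Only reading the text as a 30-day washout gives the expected result, and the words do not say that.

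**The case against.** The strongest reply is that this is a drafting slip with little practical effect. The neighbouring criteria make the intention easy to infer, and many sites would read item 21 as a 30-day washout. Established users are excluded on any of these readings. The remaining safety gap is a subject who first used an MAO inhibitor in the 30 days before screening, which is probably a small group. Item 38 may also exclude such a subject through the product label, and the full eligibility section may already be worded correctly.

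Much of this stands. The number affected is unknown and probably small. The text supplied does not state why MAO inhibitors are excluded, so treating item 21 as a safety rule is an inference. It also cannot be shown from the documents that any subject would be wrongly enrolled.

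Three things do not go away:

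- An eligibility rule should not depend on sites reading against its words. A monitor applying the text could not cite a recent-only user under item 21, and would have to cite a remote past user.
- The reach of item 38 depends on a label that is not in the documents. Whatever it covers, it only adds exclusions and cannot restore eligibility to remote past users.
- If the body text is correct, the synopsis contradicts it and still needs correcting.

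**Conclusion.** The concern holds. As written, item 21 fails to exclude subjects whose only MAO-inhibitor use is within the last 30 days and excludes remote past users with no outer limit. This follows from the ordinary meaning of the phrase and the disjunctive lead-in, and needs no assumption about prevalence.

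The size is modest. How many of the approximately 266 randomized subjects would be affected cannot be derived, and it is probably few. Sample size, power, endpoints and analysis are unaffected. The correction should still be made, because the rule gives the wrong answer when followed and costs almost nothing to put right.

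Two limits apply. Only the synopsis wording could be examined, and it is assumed that a 30-day look-back was intended, which the comparable criteria support but the sponsor must confirm.

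**What to change.** Reword item 21 on the model of item 31, for example: *Current use of an MAO inhibitor, or use of one within 30 days before screening.* The sponsor's clinical team should confirm that 30 days is the intended window. Check the version of this criterion in the protocol body and the site eligibility checklist, and align both with the corrected text.

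The cost is one line in the protocol and one in the checklist.

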## Exploratory Endpoints:

A high-contrast, black and white image showing a series of horizontal bars of varying lengths. The bars are mostly black on a white background, with some white bars appearing on the right side. A small orange dot is located at the bottom left.

	

• [REDACTED]

[REDACTED]

[REDACTED]

[REDACTED]

[REDACTED]

Statistical Methods and Planned Analyses:	The statistical analysis method for the primary endpoint is described below. Detailed analyses of secondary and exploratory endpoints will be provided in the Statistical Analysis Plan (SAP), which will be finalized before database lock and unblinding of the data.

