### **Study Populations**

The primary analysis population will be the full analysis set (FAS) excluding subjects taking rescue pain medications or second dose of study medication within the first 2 hours postdose.

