### **Primary Efficacy Analysis**

The primary efficacy analysis will be performed using Fisher's exact test.

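### Does the key secondary endpoint on the most bothersome symptom (MBS) count subjects who never had the symptom as responders?

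*Combined protocol and SAP*

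**What the plan says.** The endpoint, listed under Key Secondary Endpoints, is "The proportion of subjects who are free from their MBS among nausea, photophobia, and phonophobia 2 hours after the first dose of study medication". The matching objective, listed under Key Secondary Objectives, is "To assess the proportion of subjects with their most bothersome symptom (MBS) among nausea, photophobia, and phonophobia, absent at 2 hours postdose". Both look only at the state 2 hours after dosing.

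The two pain-free endpoints in the same part of the Synopsis are anchored to the state before dosing; each is "defined as a reduction from predose moderate [Grade 2] or severe [Grade 3] pain to none [Grade 0".

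Three other statements bear on the point:

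- Criteria for Evaluation, Efficacy, lists among the real-time eDiary items "Migraine symptoms and MBS other than pain: nausea, photophobia, and phonophobia, predose and at various timepoints postdose".
- Statistical Methods and Planned Analyses describes only the primary analysis and adds: "Detailed analyses of secondary and exploratory endpoints will be provided in the Statistical Analysis Plan (SAP"), a document to be settled before the database is locked and the blind broken.
- Study Populations reads "The primary analysis population will be the full analysis set (FAS) excluding subjects taking rescue pain medications or second dose of study medication" in the first 2 hours. It sets no condition on symptoms.

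The text does not say whether the MBS is named at screening, from history, or just before dosing in the treated attack. It also gives no scoring rule for a subject who lacks it at that moment. The remaining MBS-absent endpoint, under Other Secondary Endpoints, is partly blacked out.

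**The concern.** Treatment in the double-blind period is triggered by moderate to severe pain. No inclusion criterion requires nausea, photophobia or phonophobia in the treated attack, so some subjects may dose without their MBS. Taken word for word, such a subject is free of it at 2 hours whatever was injected. These automatic successes would appear about equally in both arms, raise both reported rates, pull the difference toward zero and cost power on a key secondary endpoint. The contrast with the pain endpoints, which do carry a predose anchor, makes the omission look like an error of definition rather than of brevity.

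**Working it through.** **Inputs from the documents.** "A total of approximately 266 subjects will be randomized in a 1:1 ratio into 2 treatment arms", so 266 / 2 = 133 per arm. The figure 266 cannot be re-derived, because the supplied text gives no response rates, power, alpha level or dropout. Fisher's exact test is named for the primary endpoint only; no test is given for the MBS endpoint.

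**Assumptions, none from the documents.** Two-sided 0.05; normal-approximation test of two proportions with pooled null variance; all 133 per arm treat an attack; true MBS-free rates among subjects with the symptom predose of pT = 52% and pC = 35%; share f without the symptom predose, equal in the two arms by randomization.

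**Formulas.** If subjects without the symptom were scored as free, each arm's rate would be f + (1 − f)p, and the difference (1 − f)(pT − pC). With d the difference and p̄ the mean of the two rates,

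power = Φ[(d − 1.96·se0)/se1], se0 = √(2p̄(1 − p̄)/n), se1 = √([pT(1 − pT) + pC(1 − pC)]/n).

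**Worked case, f = 10%.**

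- Rates: 0.10 + 0.90 × 0.52 = 0.568 and 0.10 + 0.90 × 0.35 = 0.415. The difference is 0.153 (= 0.90 × 0.17).
- se0 = √(2 × 0.4915 × 0.5085/133) = 0.0613.
- se1 = √((0.568 × 0.432 + 0.415 × 0.585)/133) = 0.0606.
- Power = Φ[(0.153 − 1.96 × 0.0613)/0.0606] = Φ(0.54) = 70.6%.
- Restricted to subjects with the symptom, n = 133 × 0.90 ≈ 120 per arm, the difference is 0.17 and power is 76.0%.

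**Range over f.**

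| f | Rates if scored as free | Difference (points) | Power, n = 133 | Power, restricted (n per arm) | Loss (points) |
|---|---|---|---|---|---|
| 0 | 52.0% vs 35.0% | 17.00 | 80.2% | 80.2% (133) | 0 |
| 2% | 52.96% vs 36.30% | 16.66 | 78.4% | 79.3% (130) | 0.9 |
| 5% | 54.40% vs 38.25% | 16.15 | 75.5% | 78.0% (126) | 2.5 |
| 10% | 56.8% vs 41.5% | 15.30 | 70.6% | 76.0% (120) | 5.4 |
| 20% | 61.6% vs 48.0% | 13.60 | 60.7% | 70.7% (106) | 10.0 |

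Other assumed rates behave alike. At f = 30%, 60% vs 40% gives 66.9% against 78.4% restricted, and 50% vs 35% gives 41.5% against 54.4%.

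**Type I error.** If pT = pC, then f + (1 − f)pT = f + (1 − f)pC. The arms stay equal under the null, so the effect is attenuation only.

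**Does the plan put f above zero and score those subjects as free?** The endpoint speaks of each subject's own MBS, which supposes that the subject has one. The eDiary item covers MBS predose. If the subject names it from the symptoms then present, it is present by construction and f = 0; a subject with none of the three symptoms has no MBS to be free of and falls outside the denominator. The text allows this reading without settling it. No sentence supports the opposite rule, that absence before dosing counts as success.

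**The case for a change.** The best case for a change is that responder status and denominator define the endpoint and are not mere analysis detail. The protocol fixes them for pain, so it should fix them for the MBS. The visible sentence is not interrupted by a redaction, and read literally it admits subjects without the symptom. The MBS might be a subject-level choice, since the eDiary also captures a migraine during screening; then f need not be zero. Even if the MBS is chosen predose, a subject with none of the three symptoms needs a rule. Scoring such subjects as failures shrinks the difference by the same (1 − f). Restricting on a status recorded before dosing keeps the randomized comparison intact and costs only wording.

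Most of this stands as a description of incomplete text. The denominator and the time at which the MBS is chosen are unwritten in what was supplied, and the direction of any dilution is right. What does not stand is the step from silence to a defect. The supplied text is the Synopsis, which defers secondary-analysis detail to a SAP written under the blind, and that is the usual place for denominators and for attacks without the baseline symptom. The predose data are collected, so the sensible rule needs no new procedure. For the other MBS-absent endpoint, the redaction rules out any statement about what is missing.

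**Conclusion.** No change to the plan follows. The Synopsis is terse on the MBS endpoint, but it does not score subjects without the symptom as responders. The natural completion, a denominator of subjects whose MBS is present before the first dose in the treated attack, can be made from data the trial already records, before unblinding.

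If the literal reading were applied instead, the harm would be conservative: a difference multiplied by (1 − f), inflated absolute rates and reduced power on a secondary endpoint, with the primary endpoint and type I error untouched. The size runs from nothing at f = 0 to about 10 power points at f = 20% on 52% vs 35%, and about 11 to 13 points at f = 30% on the other two rate pairs. Those figures rest on assumed response rates, an assumed f, two-sided 0.05 and full treatment of 133 per arm. They show what an unfavourable reading could cost, and are not evidence that the plan incurs it.
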